9.6.3 Summaries of Baseline Characteristics, Demographics, and Other Analyses

9.6.3.1 Demographic and Baseline Characteristics

The comparability of the treatment groups for each relevant demographic and baseline characteristic will be presented in tables and/or graphs. No statistical hypothesis tests will be performed on these characteristics. The number and percentage of participants randomized and the primary reason for discontinuation will be displayed. Demographic variables (such as age) and baseline characteristics will be summarized by treatment either by descriptive statistics or categorical tables.

[figure not shown]
CCI

9.8 Multiplicity

The overall type I error rate for the primary endpoint (OR) ^{CCI} [redacted] in this study will be strongly controlled at $\alpha = 2.5\%$ (one-sided) [Chen, C., et al 2018]. ^{CCI} [redacted]

[figure not shown]

The overall type I error rate across the dual primary hypotheses (ORR in participants with $CPS \geq 1$ and ORR in participants with $CPS \geq 20$) will be strongly controlled at α 2.5% (1-sided)

CCI

CCI α 1% (1-sided) will be initially allocated to ORR in participants with $CPS \geq 1$ and α 1.5% (1-sided) will be allocated to ORR in participants with $CPS \geq 20$. The graphical approach of Maurer and Bretz [Maurer, W. and Bretz, F. 2013] will be applied to reallocate alpha between the dual primary hypotheses if either primary hypothesis is rejected. According to this approach, study hypotheses may be tested more than once, and, when a particular null hypothesis is rejected, the α allocated to that hypothesis can be reallocated to other hypothesis tests. Figure 4 shows the multiplicity diagram that will be used to implement the graphical method. The initial 1-sided α allocation for each hypothesis is shown in the ellipse representing the hypothesis. The weights for reallocation from each hypothesis to the others are represented in the boxes on the lines connecting hypotheses.

Figure 4 Multiplicity Diagram

CPS combined positive scoring; H hypothesis; ORR objective response rate

CCI

9.9 Sample Size and Power Calculations

The overall sample size will be approximately CCI 200, CCI

[figure not shown]
CCI

Based on MK-3475 KN048 data, the prevalence rate of the participants with CPS ≥ 20 among participants with CPS ≥ 1 is assumed to be 50%. Table 16 provides the power to claim superior ORR of Arm 1 in participants with CPS ≥ 1 or CPS ≥ 20 if study continues to enroll up to approximately 200 participants. A study with 100 participants per arm provides approximate 84.0% power to detect a 21% difference in ORR (40% in Arm 1 vs 19% in Arm 2) at the type I error of 1% (1-sided) for participants with CPS ≥ 1 . With 50 participants per arm, the study has approximately 86.3% power to detect a 31% difference in ORR (55% in Arm 1 vs 24% in Arm 2) at the type I error of 1.5% (1-sided) for participants with CPS ≥ 20 . It has approximately 91.5% power to show that Arm 1 is superior to Arm 2 in at least 1 population (participants with CPS ≥ 1 or participants with CPS ≥ 20) at an overall type I error of 2.5% (one-sided). An observed ORR difference of approximately 15% (e.g., 34% vs. 19%) in CPS ≥ 1 or 21% (eg, 45% vs 24%) in CPS ≥ 20 is needed to achieve a positive ORR outcome. The powers to claim superior ORR of Arm 1 at the type I error of 2.5% (1-sided) are also provided in Table 16 when one of null hypotheses is rejected and the α allocated to that hypothesis is reallocated to the other hypothesis test.

Table 16 Power of ORR CCI in the Study (200 participants in total)

Hypothesis	Population	Alpha Level (one-sided)	True difference in ORR (Arm 1 versus Arm 2)	Power	Power at study level (at least one population win)
H1	CPS ≥ 1	0.010	21%	84.0%	91.5%
		0.025	21%	91.8%	
H2	CPS ≥ 20	0.015	31%	86.3%	
		0.025	31%	90.4%	

CPS combined positive scoring; H hypothesis; ORR objective response rate.
 Assume true ORR of Arm 2 is 19% and 24% in participants with CPS ≥ 1 and CPS ≥ 20 , respectively.

CCI

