9.6.1.1 Objective Response

The stratified Miettinen and Nurminen method [Miettinen, O. and Nurminen, M. 1985] will be used for the ORR comparison (Arm 1 vs Arm 2) in participants with CPS ≥ 1 and in participants with CPS ≥ 20 . The difference in ORR, 95% CI and p -values from the stratified

Miettinen and Nurminen method [Miettinen, O. and Nurminen, M. 1985] with strata weighting by sample size will be reported. The stratification factor used for randomization (Section 6.3.2) will be applied to the analysis. In the IA for continuing enrollment decision-making, the stratification will be based on PD-L1 CPS (≥ 1 to < 20 vs ≥ 20). Sensitivity analyses will be performed for comparison of ORR based on the investigator's assessment.

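### Are the 0.025 rows of Table 16 and the 95% CIs for the ORR difference inconsistent with the 1% / 1.5% alpha split?

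*Combined protocol and SAP*

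**What the plan says.** Section 9.8 controls one-sided error at 2.5% over both primary hypotheses: "The overall type I error rate across the dual primary hypotheses (ORR in participants with" CPS ≥1 and in those with CPS ≥20). H1 starts at 1% ("1% (1-sided) will be initially allocated to ORR in participants with" CPS ≥1) and H2 at 1.5% ("1.5% (1-sided) will be allocated to ORR in participants with" CPS ≥20). The graphical method "will be applied to reallocate alpha between the dual primary hypotheses if either primary hypothesis is rejected". It adds that "study hypotheses may be tested more than once, and, when a particular null hypothesis is rejected", the alpha it held can move to the other test.

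Table 16 in Section 9.9 has a column for the one-sided alpha level and two rows per hypothesis: H1 84.0% at 0.010 and 91.8% at 0.025; H2 86.3% at 0.015 and 90.4% at 0.025. A separate column gives 91.5% for a win in at least one population. The 0.025 rows are introduced with "The powers to claim superior ORR of Arm 1 at the type I error of 2.5% (1-sided) are also provided", applying "when one of null hypotheses is rejected" and its alpha reallocated.

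Section 9.6.1.1 reports "The difference in ORR, 95% CI and" p-values from the stratified Miettinen and Nurminen method. Section 9.6.1 refers to Section 9.8 for what counts as statistically significant.

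**The concern.** The sentence introducing the 0.025 rows describes what happens after one null has been rejected. A reader may therefore take 91.8% and 90.4% as power under the graphical procedure, or as power conditional on the other rejection. They are neither. Table 16 itself hints at this: a claim on H1 is a win in at least one population, so the procedure's power for H1 cannot exceed the 91.5% beside it, yet 91.8% is printed.

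The interval raises a similar doubt. A two-sided 95% CI corresponds to a one-sided 2.5% test, but H1 starts at 1% and H2 at 1.5%. An interval could exclude zero while its hypothesis is not rejected.

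At stake would be an overstated chance of a claim in each population, and a report whose intervals and tests appear to disagree.

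**Working it through.** **Inputs (Section 9.9).** H1: 100 per arm, 40% vs 19%. H2: 50 per arm, 55% vs 24%. Half of participants have CPS ≥20, so the implied rates for CPS 1–19 are 2×40% − 55% = 25% and 2×19% − 24% = 14%. Alphas come from Section 9.8. Full transfer of alpha is assumed: the Figure 4 weights are not shown, but the 0.025 level implies it.

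**Step 1: the plan's single-test figures.** With the pooled normal formula, power = Φ[(p₁ − p₂ − z·SE₀)/SE₁].

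- H1: SE₀ = √(2×0.295×0.705/100) = 0.0645; SE₁ = √((0.40×0.60 + 0.19×0.81)/100) = 0.0628.
  - At 1%: Φ[(0.21 − 2.326×0.0645)/0.0628] = 83.0%.
  - At 2.5%: Φ[(0.21 − 1.960×0.0645)/0.0628] = 90.9%.
- H2: SE₀ = √(2×0.395×0.605/50) = 0.0978; SE₁ = √((0.55×0.45 + 0.24×0.76)/50) = 0.0927.
  - At 1.5%: Φ[(0.31 − 2.170×0.0978)/0.0927] = 85.4%.
  - At 2.5%: Φ[(0.31 − 1.960×0.0978)/0.0927] = 89.9%.

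All are within 1 point of Table 16. Simulating 500,000 trials with 50 per arm in each CPS stratum comes closer:

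| | Table 16 | Pooled z | Miettinen-Nurminen, unstratified |
|---|---|---|---|
| H1 at 0.010 | 84.0% | 84.0% | 84.0% |
| H1 at 0.025 | 91.8% | 91.8% | 91.6% |
| H2 at 0.015 | 86.3% | 86.2% | 86.2% |
| H2 at 0.025 | 90.4% | 90.2% | 90.2% |
| At least one | 91.5% | 91.4% | 91.4% |

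So the 0.025 rows are correct as power of a single test at one-sided 2.5%.

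**Step 2: the two other readings** (same simulation, Miettinen-Nurminen).

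- Procedure power for H1 = P(H1 rejected at 1%, or H2 rejected at 1.5% and H1 at 2.5%) = 88.7%. The mirror image for H2 is 88.4%. Both: 85.7%. Check: 88.7 + 88.4 − 85.7 = 91.4%, the at-least-one figure.
- Conditional on the other null being rejected at its initial alpha: H1 96.8%, H2 96.5%.

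The printed values lie 3.1 and 2.0 points above the procedure reading (91.8 − 88.7; 90.4 − 88.4) and 5.0 and 6.1 points below the conditional one (96.8 − 91.8; 96.5 − 90.4). With H1 stratified by CPS, procedure power is about 89.6% and 88.6%.

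**Step 3: is the split used elsewhere?** The 0.010 and 0.015 rows and the 91.5% use it (Step 1). So do the observed differences said to be needed:

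- 34% vs 19%, 100 per arm: z = 2.40, against 2.33 for 1%.
- 45% vs 24%, 50 per arm: z = 0.21/√(2×0.345×0.655/50) = 2.21, against 2.17 for 1.5%.

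**Step 4: the interval.** With 19/100 in Arm 2, 32/100 gives p = 0.018 and 33/100 gives p = 0.012. Both meet 2.5% and miss 1%. With 12/50, 22/50 gives p = 0.018, which misses 1.5%. These results conflict with a 95% CI only if the other hypothesis is not rejected. If it is, the remaining test runs at 2.5%, all three pass, and the 95% CI agrees. Under the plan's assumptions H2 is rejected at its initial 1.5% about 86% of the time.

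**The case for a change.** The best case for a change is that neither reading the sentence invites gives the printed figures, and that 91.8% for H1 beside 91.5% for any win cannot be procedure power whatever the Figure 4 weights are. That is correct, and the sentence is loose. But the column heading says what the rows are, the numbers match it, and nothing in the plan calls them the power of the graphical procedure. Nor is there a clear direction of error, since one reading makes the figures too high and the other too low.

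On the interval, it can be said that with no effect at least one of two 95% CIs would exclude zero in favour of Arm 1 about 4.2% of the time (bivariate normal, correlation √0.5 = 0.71), against the controlled 2.5%, and that Section 9.10 calls its subgroup interval nominal while Section 9.6.1.1 does not. The 4.2% is right, but it is the error rate of a decision rule the plan does not use. Intervals at 98%, 97% or 95% according to the other test's outcome would be harder to read, and would return to two 95% CIs whenever both hypotheses are rejected.

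The power of winning both is not stated. Section 3 defines success as superiority in either population, and 91.5% is the figure for that definition.

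**Conclusion.** No change to the plan follows. Table 16 contains no numerical error: 91.8% and 90.4% are single-test powers at one-sided 0.025, as their row labels say. The alpha split is carried through in the initial-alpha powers, the study-level power and the success thresholds. The slip is clerical, a sentence in Section 9.9 that makes single-test figures sound conditional. Reading them as procedure power would overstate it by 2 to 3 points per hypothesis, but sample size, tests, alpha allocation, decision rule and the 91.5% would all stay as they are.

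The 95% CI is an estimate reported beside p-values that are judged under Section 9.8. Analysts can call it nominal in the report without amending anything.

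The procedure and conditional figures rest on full alpha transfer, an unstratified test unless stated, the plan's response rates and equal CPS strata, and no effect of the interim analysis, whose details are blacked out. The finding that the printed figures match their labels needs neither the transfer weights nor the joint distribution of the two tests.

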9.10 Subgroup Analyses

To determine whether the treatment effect is consistent across various subgroups, the estimate of the between-group treatment effect (with a nominal 95% CI) for ORR, PFS and OS will be estimated within each category of each subgroup. The following are examples of classification variables:

- Stratification factors
 - PD-L1 expression level (defined by CPS ≥ 1 to <20 vs CPS ≥ 20)
 - ECOG status (0 vs. 1)
 - HPV status as determined by p16 IHC (positive vs. negative) (for participants with oropharyngeal cancer only)
- Age category (<65 vs ≥ 65 years)
- Sex (female vs male)
- Race (white vs non-white)
- Region (North America [NAM] vs EU vs Rest of the World [ROW])
- Smoking status (never vs former vs current)
- Disease status (metastatic vs. unresectable, recurrent)

9.11 Compliance (Medication Adherence)

Drug accountability data for study intervention will be collected during the study. Any deviation from protocol-directed administration will be reported.

9.12 Extent of Exposure

The extent of exposure will be summarized as duration of treatment in number of cycles or administrations as appropriate. Summary statistics will be provided on extent of exposure for the APaT population.

10 SUPPORTING DOCUMENTATION AND OPERATIONAL CONSIDERATIONS

10.1 Appendix 1: Regulatory, Ethical, and Study Oversight Considerations

10.1.1 Code of Conduct for Clinical Trials

Merck Sharp & Dohme LLC, Rahway, NJ, USA (MSD)

Code of Conduct for Interventional Clinical Trials

I. Introduction

A. Purpose

MSD, through its subsidiaries, conducts clinical trials worldwide to evaluate the safety and effectiveness of our products. As such, we are committed to designing, implementing, conducting, analyzing, and reporting these trials in compliance with the highest ethical and scientific standards. Protection of participants in clinical trials is the overriding concern in the design and conduct of clinical trials. In all cases, MSD clinical trials will be conducted in compliance with local and/or national regulations (including all applicable data protection regulations), and International Council for Harmonisation Good Clinical Practice (ICH GCP), and also in accordance with the ethical principles that have their origin in the Declaration of Helsinki.

B. Scope

Highest ethical and scientific standards shall be endorsed for all clinical interventional investigations sponsored by MSD irrespective of the party (parties) employed for their execution (e.g., contract research organizations, collaborative research efforts). This Code is not intended to apply to trials that are observational in nature, or which are retrospective. Further, this Code does not apply to investigator initiated trials, which are not under the full control of MSD.

II. Scientific Issues

A. Trial Conduct

1. Trial Design

Except for pilot or estimation trials, clinical trial protocols will be hypothesis driven to assess safety, efficacy and/or pharmacokinetic or pharmacodynamic indices of MSD or comparator products. Alternatively, MSD may conduct outcomes research trials, trials to assess or validate various endpoint measures, or trials to determine patient preferences, etc.

The design (i.e., participant population, duration, statistical power) must be adequate to address the specific purpose of the trial. Participants must meet protocol entry criteria to be enrolled in the trial.

2. Site Selection

MSD selects investigative sites based on medical expertise, access to appropriate participants, adequacy of facilities and staff, previous performance in clinical trials, as well as budgetary considerations. Prior to trial initiation, sites are evaluated by MSD personnel (or individuals acting on behalf of MSD) to assess the ability to successfully conduct the trial.

3. Site Monitoring/Scientific Integrity

Investigative trial sites are monitored to assess compliance with the trial protocol and Good Clinical Practice (GCP). MSD reviews clinical data for accuracy, completeness, and consistency. Data are verified versus source documentation according to standard operating procedures. Per MSD policies and procedures, if fraud,

scientific/research misconduct or serious GCP non compliance is suspected, the issues are investigated. When necessary, the clinical site will be closed, the responsible regulatory authorities and ethics review committees notified.

B. Publication and Authorship

Regardless of trial outcome, MSD commits to publish the primary and secondary results of its registered trials of marketed products in which treatment is assigned, according to the pre specified plans for data analysis. To the extent scientifically appropriate, MSD seeks to publish the results of other analyses it conducts that are important to patients, physicians, and payers. Some early phase or pilot trials are intended to be hypothesis generating rather than hypothesis testing; in such cases, publication of results may not be appropriate since the trial may be underpowered and the analyses complicated by statistical issues such as multiplicity.

MSD's policy on authorship is consistent with the recommendations published by the International Committee of Medical Journal Editors (ICMJE). In summary, authorship should reflect significant contribution to the design and conduct of the trial, performance or interpretation of the analysis, and/or writing of the manuscript. All named authors must be able to defend the trial results and conclusions. MSD funding of a trial will be acknowledged in publications.

III. Participant Protection

A. Regulatory Authority and Ethics Committee Review (Institutional Review Board [IRB]/Independent Ethics Committee [IEC])

All protocols and protocol amendments will be submitted by MSD for regulatory authority acceptance/authorization prior to implementation of the trial or amendment, in compliance with local and/or national regulations.

The protocol, protocol amendment(s), informed consent form, investigator's brochure, and other relevant trial documents must be reviewed and approved by an IRB/IEC before being implemented at each site, in compliance with local and/or national regulations. Changes to the protocol that are required urgently to eliminate an immediate hazard and to protect participant safety may be enacted in anticipation of ethics committee approval. MSD will inform regulatory authorities of such new measures to protect participant safety, in compliance with local and/or national regulations.

B. Safety

The guiding principle in decision making in clinical trials is that participant welfare is of primary importance. Potential participants will be informed of the risks and benefits of, as well as alternatives to, trial participation. At a minimum, trial designs will take into account the local standard of care.

All participation in MSD clinical trials is voluntary. Participants enter the trial only after informed consent is obtained. Participants may withdraw from an MSD trial at any time, without any influence on their access to, or receipt of, medical care that may otherwise be available to them.

C. Confidentiality

MSD is committed to safeguarding participant confidentiality, to the greatest extent possible. Unless required by law, only the investigator, Sponsor (or individuals acting on behalf of MSD), ethics committee, and/or regulatory authorities will have access to confidential medical records that might identify the participant by name.

D. Genomic Research

Genomic research will only be conducted in accordance with a protocol and informed consent authorized by an ethics committee.

IV. Financial Considerations

A. Payments to Investigators

Clinical trials are time and labor intensive. It is MSD's policy to compensate investigators (or the sponsoring institution) in a fair manner for the work performed in support of MSD trials. MSD does not pay incentives to enroll participants in its trials. However, when enrollment is particularly challenging, additional payments may be made to compensate for the time spent in extra recruiting efforts.

MSD does not pay for participant referrals. However, MSD may compensate referring physicians for time spent on chart review and medical evaluation to identify potentially eligible participants.

B. Clinical Research Funding

Informed consent forms will disclose that the trial is sponsored by MSD, and that the investigator or sponsoring institution is being paid or provided a grant for performing the trial. However, the local ethics committee may wish to alter the wording of the disclosure statement to be consistent with financial practices at that institution. As noted above, all publications resulting from MSD trials will indicate MSD as a source of funding.

C. Funding for Travel and Other Requests

Funding of travel by investigators and support staff (e.g., to scientific meetings, investigator meetings, etc.) will be consistent with local guidelines and practices.

V. Investigator Commitment

Investigators will be expected to review MSD's Code of Conduct as an appendix to the trial protocol, and in signing the protocol, agree to support these ethical and scientific standards.

10.1.2 Financial Disclosure

Financial Disclosure requirements are outlined in the US Food and Drug Administration Regulations, Financial Disclosure by Clinical Investigators (21 CFR Part 54). It is the Sponsor's responsibility to determine, based on these regulations, whether a request for Financial Disclosure information is required. It is the investigator's/subinvestigator's responsibility to comply with any such request.

The investigator/subinvestigator(s) agree, if requested by the Sponsor in accordance with 21 CFR Part 54, to provide his/her financial interests in and/or arrangements with the Sponsor to allow for the submission of complete and accurate certification and disclosure statements. The investigator/subinvestigator(s) further agree to provide this information on a Certification/Disclosure Form, commonly known as a financial disclosure form, provided by the Sponsor. The investigator/subinvestigator(s) also consent to the transmission of this information to the Sponsor in the United States for these purposes. This may involve the transmission of information to countries that do not have laws protecting personal data.

10.1.3 Data Protection

The Sponsor will conduct this study in compliance with all applicable data protection regulations.

Participants will be assigned a unique identifier by the Sponsor. Any participant records or datasets that are transferred to the Sponsor will contain the identifier only; participant names or any information that would make the participant identifiable will not be transferred.

The participant must be informed that his/her personal study-related data will be used by the Sponsor in accordance with local data protection law. The level of disclosure must also be explained to the participant.

The participant must be informed that his/her medical records may be examined by Clinical Quality Assurance auditors or other authorized personnel appointed by the Sponsor, by appropriate IRB/IEC members, and by inspectors from regulatory authorities.

10.1.3.1 Confidentiality of Data

By signing this protocol, the investigator affirms to the Sponsor that information furnished to the investigator by the Sponsor will be maintained in confidence, and such information will be divulged to the IRB, IEC, or similar or expert committee; affiliated institution and employees, only under an appropriate understanding of confidentiality with such board or committee, affiliated institution and employees. Data generated by this study will be considered confidential by the investigator, except to the extent that it is included in a publication as provided in the Publications section of this protocol.

